**VITAMIN D LEVELS IN UMBILICAL CORD AND ITS IMPACT ON
INFANT AND CHILDREN'S HEALTH: A COHORT STUDY (VITADi
STUDY)**

April 2022

VITAMIN D LEVELS IN UMBILICAL CORD AND ITS IMPACT ON INFANT AND CHILDREN'S HEALTH: A COHORT STUDY (VITADi STUDY)

Protocol

Responsible Personnel

Principal Investigator Contact Information

Name: [name]

Title: MD

Institution: Department of Pediatrics, Faculty of Medicine, Hasanuddin University

Address: [name]

[contact]

Email: [contact]

Other Contact

Name: [name]

Title: MD, PhD

Institution: Allergy and Immunology Division, Department of Pediatrics, Faculty of Medicine, Hasanuddin University

Address: [name]

[contact]

Email: [contact]

Summary:

This study is a cohort study that aims to assess the relationship between Vitamin D levels in infants and children, and the risk of anemia, atopic dermatitis, diarrhea and cardiovascular disorders in newborn. The subjects of this study are 100 women who met the inclusion criteria, which are in their third semester of pregnancy and agree to be included in this study with their babies. These subjects then will be examined for their weight, height and upper arm circumference using standardized CEBA digital scale, and blood sampling will also be done to these women to measure their vitamin D levels, calcium, parathyroid hormone, ferritin, Fe serum, IL-16, and IL-10. When subjects give birth, the babies will also be included in this study. Anthropometric examination will also be done on the babies, to measure their birth weight, birth length, and head circumference. Blood samples will also be taken from their umbilical cord to assess their complete blood count, ferritin, Fe serum, vitamin D levels, vitamin D receptors, IL-6 and IL-10. All subjects then will be monitored, and home visits will be done when the babies reach 3 months old and 6 months old. An assessment of the incidence of diarrhea, atopic dermatitis, and an assessment of cardiovascular disorders (checking pulse and blood pressure) will be carried out during the visit. At the end of the study, venous blood sampling will be taken to see levels of Vitamin D, calcium, parathyroid hormone, routine complete blood count, serum Fe, and ferritin, then data analysis is performed.

Introduction:

Vitamin D is essential for development, growth and the maintenance of the bone. (Huang et al., 2021) Although the main role of vitamin D is to maintain calcium homeostasis, vitamin D also has many roles in various organ system, including the immune system. The presence of vitamin D receptor (VDR) expression in immune system experimentally proves that vitamin D also plays an essential role in innate and adaptive immune system. Vitamin D is involved in immune system through intracellular VDR in monocyte/macrophage, T cells, B cells, natural killer cells (NK), and dendritic cells (DC). (Cyprian et al., 2019)

The presence of vitamin D receptors in the immunologic system, confers huge influence on the incidence of infectious diseases and allergies, such as diarrhea and atopic dermatitis. (Aluisio et al., 2013) (El Taieb, 2013, Kim JM, 2016) Epidemiological literature also explains that both vitamin D deficiency and insufficiency contribute to the incidence of cardiovascular disease and the incidence of metabolic syndrome, namely hypertension, obesity, insulin resistance and glucose intolerance. (Adams & Hewison, 2010) Several epidemiological studies and clinical trials also have found that vitamin D plays a role in iron homeostasis and erythropoiesis, hence the causal relationship with anemia. (Uwaezuoke, 2017)

The vitamin D levels of the intrauterine fetus is completely influenced by maternal vitamin D levels. 25-OH Vitamin D will go through the placental barrier and then into the baby's circulatory system with a half-life of about 2 months. (Wierzejska et al., 2017) There are several factors that influence vitamin D levels, such as maternal nutritional status, intake of calcium and phosphorus, maternal body mass index, and socioeconomic factors, meanwhile the main sources of vitamin D are sun exposure, food intake, supplementation, and fortified foods. (Holick, 2007)

Indonesia is a tropical country with high levels of sun exposure, but in fact vitamin D deficiency is still a problem that persists in the country. Data shows that children aged 2-12.9 years in Indonesia experience vitamin D insufficiency as much as 45.1%. (Koon Poh et al., 2016) The prevalence of pregnant women suffering from vitamin D deficiency is also quite high. (Adams & Hewison, 2010; Ayu Krisna Cahyaning Putri et al., nd; Cerami, 2017) This also increases the incidence of this micronutrient deficiency in newborns which can affect the growth and development of children later. Lack of vitamin D can also increase the likelihood of children suffering from several diseases later in life. By looking at the importance of vitamin D, researchers are interested in assessing the extent of the influence of maternal vitamin D levels on neonatal vitamin D levels, and how this vitamin D status affects the physical condition of the child later. This study also aims to see the effect of sun exposure on children's physical status.

Objectives:

1. General Objectives

- a. To assess the relationship between neonatal vitamin D levels to the risk of anemia, atopic dermatitis, diarrhea, and cardiovascular disorders in newborns.

2. Specific Objectives

- a. To determine the third trimester pregnant women who do not have chronic infectious diseases and hypertension.

- b. Measure the weight, height, and upper arm circumference of third trimester pregnant women.
- c. Measure vitamin D levels, calcium, parathyroid hormone, ferritin, serum iron, routine blood, IL-16, and IL-10 in third trimester pregnant women.
- d. Measure weight, body length, head circumference of newborns (whose mothers have been selected as research subjects)
- e. Measure vitamin D levels, vitamin D receptors, IL-6, and IL-10 from umbilical cord blood of newborns (whose mothers have been selected as research subjects).
- f. Monitor weight, body length, head circumference when the baby is 3 months old.
- g. Monitor weight, body length, head circumference when the baby is 6 months old.
- h. Measure levels of vitamin D, calcium, parathyroid hormone, ferritin, serum iron, routine blood, IL-6, and IL-10 when the baby is 6 months old.
- i. Measure IgE levels when the baby is 6 months old.
- j. Assess the incidence of diarrhea frequency in infants during monitoring.
- k. Assess the incidence of atopic dermatitis in infants during monitoring.
- l. Assess the incidence of hypertension during monitoring.
- m. Check the levels of vitamin D, ferritin, hemoglobin, and reticulocytes when the baby is 6 months old.
- n. Compare vitamin D levels in the umbilical cord blood of newborns with vitamin D levels at the age of 6 months.

Trial Design:

Observational study

Study Population

Women in third trimester of pregnancy in Makassar, Surabaya, Mataram who are selected during the screening test.

Number of Samples

100 samples.

Inclusion Criteria

- a. Pregnant Women
 - Women in third trimester of pregnancy
 - Agree to take blood samples and are willing to include their babies as samples for the next study.
- b. Infants
 - Babies born from mothers who are willing to be included in the study
 - Aterm
 - Birth weight > 2500 grams

Exclusion Criteria

[figure not shown]
- a. Pregnant women
 - History of abortion in previous pregnancy
 - Suffering from hypertension or preeclampsia
- b. Infants
 - Infants with congenital abnormalities at birth
 - Infants with acute infection at birth

Procedures:

1. Sampling will be preceded by giving explanations to the parents, then parents will fill and sign the informed consent paper if they agree to participate in this study.
2. All pregnant women who met the requirements as research subjects will be recorded by their name, age, parity, birth history, and history of illness.
3. Anthropometric measurements will be performed on pregnant women who met the criteria, including body weight using standardized digital CEBA scales, height, and upper arm circumference.
4. The pre-analytic in this study is the preparation of tools and materials to take 3 cc of blood serum samples (2 tubes for 1 patient), purple capped tubes (with EDTA) for routine blood count tests, and red tubes for ferritin, Fe serum, vitamin D levels, calcium, parathyroid hormone, IL-6, and IL-10.
5. After the mother gives birth, the baby who are qualified based on the inclusion criteria will also be included.
6. Birth weight, birth length and head circumference will be measured.
7. The pre-analytic in this study is the preparation of tools and materials for blood and serum sampling, collection of infants blood samples from the umbilical cord and children from venous blood (2 tubes for 1 patient), purple capped tubes (with EDTA) for routine blood count tests, and red tubes for ferritin, Fe serum, vitamin D levels, vitamin D receptors, IL-6, and IL-10. The amount of blood samples taken for the purple closed tube is 1.5 ml and for the red tube is 1.5 ml (which is the minimum value for each tube for examination).
8. Monitoring will be carried out until the baby is 6 months old. Visits will be made when the baby reach 3 months and 6 months old. Anthropometric status measurements will be done on infants to measure their weight, length, and head circumference, then we will determine the nutritional status by plotting to the WHO curve. There will be interviews with the parents/caregivers regarding complaints of diarrhea and signs of allergies such red rash and an assessment based on Hanifin Rajka's criteria will be made.
9. At the age of 6 months, a blood sample will be taken again. The pre-analytic in this study is the preparation of tools and materials for blood and serum sampling, collection of blood samples for infants from the umbilical cord and children from venous blood (2 tubes for 1 patient), purple capped tubes (with EDTA) for routine blood tests, and red tubes for examination of ferritin, serum Fe, levels of vitamin D, IL-6, and IL-10. The number of blood samples taken for the purple closed tube is 1.5 ml and for the red tube it is 1.5 ml (which is the minimum value for each tube for examination).

10. Unpleasant sensations like pain during blood sampling and fear of being stabbed with a needle will be minimized by using experts in this field, such as laboratory assistant and a doctor as a companion.

Workflow

Data Analysis

The collected data are grouped based on the purpose and type of data, then the suitable statistical methods are used, namely:

- a. Univariate analysis
Used to describe the characteristics of the basic data, in the form of frequency, mean value, standard deviation, and range.
- b. Bivariate analysis
 - 1) Wilcoxon test: Used to analyse data with independent variables with an ordinal/numeric scale, the data are not normally distributed and have different variances.

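### Cord-derived vitamin D is largely cleared by 6 months on the protocol's own half-life, but no readable procedure records the infant's postnatal sources, so the cord-to-6-month change and later associations cannot be explained

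*Combined protocol and SAP*

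**What the plan says.** All references are to the combined protocol and SAP.

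- **Half-life and sources (Introduction).** "25-OH Vitamin D will go through the placental barrier and then into the baby's circulatory system with a half-life of about 2 months". The same paragraph says that "the main sources of vitamin D are sun exposure, food intake, supplementation, and fortified foods".
- **Aims.** The general objective is "To assess the relationship between neonatal vitamin D levels to the risk of anemia, atopic dermatitis, diarrhea, and cardiovascular disorders in newborns". Specific objective n is "Compare vitamin D levels in the umbilical cord blood of newborns with vitamin D levels at the age of 6 months". The Introduction adds: "This study also aims to see the effect of sun exposure on children's physical status".
- **Follow-up (Procedures, step 8).** "Visits will be made when the baby reach 3 months and 6 months old". At these visits infants are measured, and "There will be interviews with the parents/caregivers regarding complaints of diarrhea and signs of allergies such red rash". The Summary adds pulse and blood pressure.
- **Vitamin D in the infant.** It is measured in cord blood and again at 6 months (objectives e, h and m; Procedures steps 7 and 9). No sample is described at 3 months.
- **Maternal data (Procedures, steps 2 to 4).** Women "will be recorded by their name, age, parity, birth history, and history of illness", and they have anthropometry and blood tests.
- **Data Analysis.** Descriptive statistics, a Wilcoxon test and a Mann-Whitney test. No covariates, age windows or role for the 6-month vitamin D value are given.

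**The concern.** The exposure in the general objective is fixed at birth, while outcomes accrue over 6 months. On the protocol's half-life, the infant's vitamin D passes during that time from mainly placental supply to mainly postnatal supply. The protocol names the postnatal sources and makes one of them, sun exposure, an aim. Yet the readable procedures do not ask about any of them for the infant.

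Three interpretations are at stake:

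1. A rise or fall from cord to 6 months could reflect feeding, supplements, sun or remaining cord supply, with no data to tell them apart.
2. If cord level shows no association with outcomes in months 3 to 6, one cannot tell an absent effect from an early difference that postnatal supply has since overridden.
3. If there is an association, it may run through postnatal supply. The Introduction lists maternal nutritional status and socioeconomic factors among the influences on vitamin D. These can persist after birth and link cord level to later intake.

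Feeding and supplement history not taken at the visits is hard to recover reliably afterwards, so this affects what is collected as well as how it is analysed.

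**Working it through.** The documents state no residual share, so there is no figure of the plan's to reproduce. The half-life is an input.

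**Inputs**
- Half-life h: about 2 months (Introduction).
- Visits and end of follow-up: 3 and 6 months (Procedures, step 8).
- Assumed: first-order decay, and a range of 1.5 to 3 months around the stated half-life.

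**Share of cord-derived vitamin D remaining at time t:** 0.5^(t/h)
- 3 months: 0.5^(3/2) = 0.354, or 35%.
- 6 months: 0.5^(6/2) = 0.5^3 = 0.125, or 12.5%.

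**Sensitivity to the half-life**

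| Half-life (months) | Left at 3 months | Left at 6 months |
|---|---|---|
| 1.5 | 25.0% | 6.3% |
| 2 | 35.4% | 12.5% |
| 2.5 | 43.5% | 19.0% |
| 3 | 50.0% | 25.0% |

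**Mean share over a window from a to b:** (0.5^(a/h) − 0.5^(b/h)) / (k(b − a)), with k = ln 2 / 2 = 0.3466 per month
- Months 0–3: (1 − 0.3536) / (0.3466 × 3) = 0.622, or 62%.
- Months 3–6: (0.3536 − 0.125) / (0.3466 × 3) = 0.220, or 22%.
- Months 0–6: (1 − 0.125) / (0.3466 × 6) = 0.421, or 42%.

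The two inter-visit windows therefore differ almost threefold in mean remaining cord supply (62 / 22 = 2.8).

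These figures describe only the surviving cord-derived part. The 6-month total is that part plus whatever came from food, supplements and sun. Dilution by growth is ignored and would lower the cord-derived concentration further.

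**Sources named against items recorded for the infant (readable text)**

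| Source named in the Introduction | Recorded for the infant? |
|---|---|
| Sun exposure (also a stated aim) | No item found |
| Food intake, fortified foods | No item found for feeding mode, formula or solids |
| Supplementation | No item found |

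I give no figure for the correlation between cord level and 6-month level. It would depend on how far postnatal supply tracks cord level, which the documents do not say.

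**The case against.** The strongest defence has four parts.

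- **Objective n asks only for a comparison.** This stands. Two measurements per infant allow it to be done as written, and the protocol does not claim that neonatal status persists. What is missing is the means to explain the result.
- **Vitamin D is measured again at 6 months, which captures net postnatal supply.** This stands in part. The value gives the level but not its source, and Data Analysis assigns it no role. It is taken at the end of the 3–6 month window, so it follows many of the events it would be used to explain.
- **A relationship with cord level does not need cord vitamin D to persist.** This stands. An early-life effect could show itself later, and on average 22% of the cord-derived supply is still present over months 3 to 6. The limit is on attribution; the association itself can be estimated.
- **Assessment at both visits already allows a split by age.** This stands as a matter of feasibility for diarrhea and atopic dermatitis. The plan simply does not specify the split.

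Four stronger readings are tempting, and the documents do not support them. A reader might infer that the infant's vitamin D level falls to 12.5%; that share applies only to the cord-derived part. A reader might infer that outcomes will be pooled into one 0–6 month block; the objectives speak of monitoring in general and no text commits to pooling. A reader might infer that feeding alone would produce a cord–outcome association; that needs feeding to be related both to cord level and to the outcome, which is plausible but is not stated. Finally, a reader might conclude that postnatal sources are definitely not collected; the Workflow figure is not shown and may list more items.

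**Conclusion.** The point holds as a limit on interpretation. On the stated half-life, about 35% of cord-derived vitamin D remains at 3 months and 12.5% at 6 months (6% to 25% for an assumed half-life of 1.5 to 3 months). Across that whole range most of the cord supply has gone by the last visit, so the conclusion does not hang on exactly 2 months. As the readable text stands, the study can report the cord-to-6-month change but cannot explain it. It can estimate associations between cord level and outcomes in months 3 to 6 but cannot separate them from postnatal supply.

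This rests on first-order decay and on the Workflow figure not listing the missing items. It does not invalidate the study or rule out an early-life effect of cord status. It is a worthwhile change because it is cheap and because the missing data cannot be collected reliably later.

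**What to change.** 1. **Procedures, step 8.** Add to the existing 3- and 6-month caregiver interviews: feeding mode, age when formula and solids were started, any vitamin D or iron supplement given to the infant, and the infant's sun exposure. If the Workflow figure already includes these items, bring them into the text.
2. **Objective n.** Report the paired cord-to-6-month comparison overall and by feeding and supplement group, described as postnatal change.
3. **Data Analysis.** Report the association of cord vitamin D with diarrhea, atopic dermatitis and 6-month anemia, stratified by or adjusted for feeding and supplements. Add a sensitivity analysis that includes the 6-month vitamin D level, noting that it may be a mediator and so should not replace the main result.
4. **Age windows.** Report diarrhea and atopic dermatitis for 0–3 and 3–6 months beside the 0–6 month result. This does not apply to anemia, since infant blood is taken only at birth and at 6 months.

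**Cost.** A few questions at two visits already planned, and some extra tables. The real price is precision: with about 100 infants, each window or stratum will hold fewer events, so the split results should be read as descriptive and the 0–6 month result kept alongside them.

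### The sun-exposure aim has no exposure data in the written plan, and cord vitamin D is tested against infant outcomes without adjustment, so the results can be read only as associations

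*Combined protocol and SAP*

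**What the plan says.** **Sun exposure.** The last sentence of the Introduction states an aim: "This study also aims to see the effect of sun exposure on children's physical status". It does not say whether the mother's or the infant's exposure is meant.

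**Causes of vitamin D.** The Introduction also says "The vitamin D levels of the intrauterine fetus is completely influenced by maternal vitamin D levels". It lists influences, among them "maternal body mass index, and socioeconomic factors", and adds that "the main sources of vitamin D are sun exposure, food intake, supplementation, and fortified foods".

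**What is recorded.**
- Procedure 2: eligible women "will be recorded by their name, age, parity, birth history, and history of illness".
- Procedure 3: maternal measurements, "including body weight using standardized digital CEBA scales, height, and upper arm circumference".
- Objective c and procedure 4: maternal vitamin D, calcium, parathyroid hormone, ferritin, serum iron and a routine blood count.
- Study Population: "Women in third trimester of pregnancy in Makassar, Surabaya, Mataram who are selected during the screening test". City is therefore known from the recruiting site.
- Procedure 8, at 3 and 6 months: infant growth plotted on the WHO curve, and an interview described as "There will be interviews with the parents/caregivers regarding complaints of diarrhea and signs of allergies".

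**Analysis.** Data Analysis has a descriptive part and a bivariate part (Wilcoxon and Mann-Whitney tests). It describes no regression or stratification.

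**The concern.** There are two gaps. First, a stated aim has no exposure variable behind it. If the plan is followed as written, there will be nothing to analyse for sun exposure at the end.

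Second, a mother's income, diet or supplement habits can alter her vitamin D, and so the cord level. They can also reach infant anemia, diarrhea or atopic dermatitis by routes that do not involve vitamin D. A two-group comparison of cord vitamin D cannot separate these routes.

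The general objective asks only about a *relationship*, and a crude comparison can address that. The title speaks of *impact*, and the Introduction of how vitamin D status *affects* the child. Unadjusted tests cannot carry those words. Background items not asked at enrolment can be recovered later only by recall.

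**Working it through.** The plan gives no figure to reproduce: the sample of 100 comes without effect size, event rate, power or dropout. The check is a comparison of sections, followed by illustrations on assumed inputs.

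**1. Sun exposure.** It appears in none of objectives a–n, procedures 1–10, the blood panels or Data Analysis.

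**2. Named causes against recorded items.**

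| Named in the Introduction | Listed for recording? | Adjusted for? |
|---|---|---|
| Maternal nutritional status | Yes, from arm circumference and weight | No |
| Maternal BMI | Yes, from weight and height | No |
| Calcium and phosphorus intake | No (serum calcium is not intake) | No |
| Socioeconomic factors | No | No |
| Sun exposure | No | No |
| Food intake | No | No |
| Supplementation | No | No |
| Fortified foods | No | No |

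Of 8, 2 are recorded, 6 are not, and 0 are adjusted for. Outside this list, age, parity, illness history, city and the maternal blood results are available. None is used for adjustment.

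**3. Possible bias in a risk ratio (all inputs assumed).** Suppose cord vitamin D has no effect. An unrecorded factor multiplies outcome risk by R, and is present in a fraction p1 of low-vitamin-D infants and p0 of the others. The crude risk ratio is then [1 + p1(R − 1)] / [1 + p0(R − 1)].
- p1 = 0.5, p0 = 0.3, R = 1.5: 1.25 / 1.15 = 1.09.
- p1 = 0.7, p0 = 0.3, R = 3: 2.4 / 1.6 = 1.50.

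**4. Possible false-positive rate (all inputs assumed).** One unrecorded cause has correlation L with both cord vitamin D and hemoglobin, and there is no true effect. The induced correlation is L². Anemia affects 20–50% of infants, and the test is Mann-Whitney at p ≤ 0.05. There were 4,000 simulated studies per cell (Monte Carlo error about 0.3–0.8 points). The 100 in the plan are women and some infants will be excluded, so 70 infants is shown as a second assumption.

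| L | L² | 100 infants | 70 infants |
|---|---|---|---|
| 0.2 | 0.04 | 5.2–6.0% | 5.5–5.7% |
| 0.3 | 0.09 | 9.4–10.1% | 8.0–8.2% |
| 0.4 | 0.16 | 19.4–23.1% | 13.8–17.2% |
| 0.5 | 0.25 | 41.1–48.8% | 27.9–36.6% |

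**5. What adjustment recovers.** With 100 infants, logistic regression adjusting for the cause gives 4.2–5.2% if it is recorded without error. At L = 0.5 it gives 8.8–10.4% if the question has reliability 0.7, and 19.1–23.6% at reliability 0.4.

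**6. Room for covariates in binary outcomes.** Take 10 events per parameter (a rule of thumb, not in the documents) and reserve one parameter for cord vitamin D. Then 20, 30 and 50 events among 100 infants leave 1, 2 and 4 covariate parameters. With 70 infants at the same rates, 14, 21 and 35 events leave 0, 1 and 2. City, with three sites, uses 2.

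**The case against.** **The stated objective is not contradicted.** The design is labelled observational, and a crude association answers a question about a relationship. This stands. The conflict is with the wording of the title and Introduction, not with the general objective.

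**Much is already recorded.** A reader might infer that the plan collects nothing on maternal causes. It does not support that. Maternal vitamin D, ferritin, serum iron and blood count are all measured, and iron status is an obvious candidate cause for anemia. The gap in recording is confined to socioeconomic, dietary, supplement and sun items; the gap in use covers everything. Measuring maternal vitamin D does not settle the matter. Conditioning on it would close the path through maternal vitamin D, but on the Introduction's own premise it would leave little cord variation to study.

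**The sun sentence is one line outside the Objectives.** True, and deleting it cures the mismatch. But it is worded as an aim, so it should be either supported or removed.

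**Adjustment may often be impossible.** With few events, a logistic model has no room. This stands for binary outcomes. It does not apply to 6-month hemoglobin (objective m) or blood pressure (Summary), which are continuous.

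**Items may exist elsewhere.** The Workflow content is not shown and no questionnaire is included. A reader might conclude that sun exposure will certainly go unmeasured; the documents show only that the written plan does not list it. Equally, the reference list holds a paper on multivariable prognostic models, but Data Analysis describes no such model.

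**Conclusion.** Both gaps hold for the written plan. The sun-exposure aim cannot be answered as written. The cord vitamin D results will be crude associations: suitable for the general objective, insufficient for the causal wording elsewhere.

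The size of any bias is unknown, because the documents give no correlations or event rates. The simulated rates rest on one shared cause, no true effect and assumed anemia frequencies. They show that a weak shared cause hardly matters and a strong one does. Two stronger readings are not supported:

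- **That the cord results will be badly biased.** The figures above 40% need a single cause explaining a quarter of the variance (0.5² = 0.25) in both cord vitamin D and hemoglobin. Nothing in the documents establishes this.
- **That infant feeding, supplements and sun confound the cord association.** They follow the cord sample. They are separate causes of the 6-month results and share background with cord vitamin D only through the family.

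**What to change.** 1. **Sun aim.** Either add short infant sun-exposure items to the 3- and 6-month interviews (procedure 8) and report their association with the WHO-curve growth status already collected, with its limits, or delete the sentence. If it is kept, state whose exposure is meant.
2. **Enrolment record (procedure 2).** Add maternal education or income, diet including fortified foods, and use of vitamin D and iron supplements.
3. **Analysis.** Keep the bivariate tests. Add one prespecified adjusted analysis of cord vitamin D per main outcome, with a small set of pre-birth covariates that plausibly reach that outcome other than through vitamin D. Examples are maternal iron status for anemia, education or income, maternal BMI or age, and city. Do not include maternal sun exposure by default: no second path to the outcomes is argued, and adjusting for it would mainly remove variation in the exposure. Do not adjust for post-birth infant feeding or supplements as confounders.
4. **Model form.** Use linear models for hemoglobin and blood pressure, so that adjustment does not depend on event counts. For binary outcomes with too few events, report the result as unadjusted.
5. **Wording.** Describe all results as associations.

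If enrolment is already complete, the recorded covariates, the deletion and the wording change remain available.

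**Cost.** A few questions at contacts already scheduled and one small analysis per main outcome, with no new visit or blood sample. Interviews become slightly longer, recall error leaves some residual confounding, and at most about 100 infants allow only a few covariates.

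### Iron could create or hide an association between cord vitamin D and 6-month anemia: intake is not recorded, and the cord and maternal iron measurements have no role in the analysis

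*Combined protocol and SAP*

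**What the plan says.** The general objective is "To assess the relationship between neonatal vitamin D levels to the risk of anemia, atopic dermatitis, diarrhea, and cardiovascular disorders in newborns". For the 6-month visit, Specific Objective m says "Check the levels of vitamin D, ferritin, hemoglobin, and reticulocytes when the baby is 6 months old", and objective h adds serum iron and a routine blood count.

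On iron intake the text is silent. Procedures step 2 says that mothers "will be recorded by their name, age, parity, birth history, and history of illness". Step 8 says of follow-up: "There will be interviews with the parents/caregivers regarding complaints of diarrhea and signs of allergies such red rash". No eligibility criterion mentions iron.

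On iron status at birth, the Summary says "Blood samples will also be taken from their umbilical cord to assess their complete blood count, ferritin, Fe serum". Step 7 agrees: the EDTA tube is for the blood count, and the other is described as "red tubes for ferritin, Fe serum, vitamin D levels, vitamin D receptors, IL-6, and IL-10". Specific Objective e is narrower: "Measure vitamin D levels, vitamin D receptors, IL-6, and IL-10 from umbilical cord blood of newborns". Objective c has ferritin, serum iron and a blood count measured in the mothers in the third trimester.

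The only cord-to-6-month comparison listed (objective n) is for vitamin D itself. Data Analysis consists of descriptive statistics, a Wilcoxon test and a Mann-Whitney test, with no adjusted or stratified analysis.

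**The concern.** This is an observational cohort, so infants with low and high cord vitamin D may differ in other ways. The Introduction names diet, supplements and fortified foods among the main sources of vitamin D, and lists maternal nutrition and socioeconomic factors as influences on its level. The same things can plausibly govern iron. Iron bears directly on hemoglobin and ferritin.

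If iron does travel with vitamin D, a two-group test at 6 months cannot tell a vitamin D effect from iron status already present at birth or from iron given afterwards. The error can go either way. Iron status at birth could be examined with data the study already plans to hold. Infant intake after birth is wholly unmeasured, and if it is not asked about at the visits it can be recovered later only by longer recall.

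**Working it through.** **Plan's own figure.** The sample size is 100, with no effect size, event rate, exposure split or power stated, so there is nothing to reproduce. Every input below except 100 and the 0.05 level is an assumption.

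**1. Iron status at birth.** Let *a* be the correlation of cord iron status with cord vitamin D, and *b* its correlation with 6-month hemoglobin. Set the vitamin D effect to zero and split infants at the vitamin D median. The spurious difference in mean hemoglobin is 2ab√(2/π) SD.
- a = 0.2, b = 0.3: 2 × 0.06 × 0.798 = 0.10 SD.
- a = 0.5, b = 0.5: 2 × 0.25 × 0.798 = 0.40 SD.

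A simulation of this model (3,000 runs per setting) gave these rejection rates at 0.05 for 100 infants:

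| a | b | Mann-Whitney, unadjusted | Linear model with cord iron |
|---|---|---|---|
| 0 | 0.5 | 0.049 | 0.047 |
| 0.2 | 0.3 | 0.077 | 0.050 |
| 0.3 | 0.5 | 0.200 | 0.051 |
| 0.4 | 0.5 | 0.349 | 0.045 |
| 0.5 | 0.5 | 0.497 | 0.047 |

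With 80 infants the unadjusted rate runs from 0.061 (a = 0.2, b = 0.3) to 0.405 (a = b = 0.5). The adjusted column is a best case, because in this model all the confounding passes through a cord value measured without error.

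**2. Iron intake, hemoglobin scale.** If intake raises hemoglobin by *e* SD, the bias is e × (uptake in high group − uptake in low group). With 50 infants per group and no vitamin D effect:
- 60% vs 40%, e = 0.5: 0.5 × 0.2 = 0.10 SD; 7% false positives.
- 70% vs 30%, e = 0.8: 0.8 × 0.4 = 0.32 SD; 31%.
- 80% vs 20%, e = 0.8: 0.8 × 0.6 = 0.48 SD; 61%.

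**3. Iron intake, risk scale.** Suppose anemia is 10% with iron and 30% without, whatever the vitamin D level.
- Uptake 60% (high vitamin D) vs 30% (low): 0.6 × 0.10 + 0.4 × 0.30 = 18%; 0.3 × 0.10 + 0.7 × 0.30 = 24%. Ratio, low to high, 24/18 = 1.33.
- Uptake 70% vs 20%: 16% and 26%; ratio 26/16 = 1.63.
- Equal uptake: ratio 1.00.
- Uptake reversed, 30% vs 60%: ratio 18/24 = 0.75, so a real harm of low vitamin D would be masked.

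For scale, 24% vs 18% with 50 per group is 12 vs 9 cases. The standard error of the log ratio is √(1/12 − 1/50 + 1/9 − 1/50) = 0.393, so the 95% interval around 1.33 is about 0.62 to 2.9. At these rates, with about an 11% chance of p < 0.05, the bias would distort the estimate more often than it produced a significant result.

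**4. Precision of the adjusted analysis.** Adjustment lowers residual variance to 1 − b² but inflates the variance of the vitamin D coefficient by 1/(1 − a²). The unadjusted residual variance is 1 − a²b².
- a = 0.2, b = 0.5: 0.75/0.96 = 0.78 against 0.99, a gain.
- a = 0.5, b = 0.3: 0.91/0.75 = 1.21 against 0.98, a loss.

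**The case against.** The strongest objection is over-adjustment. The Introduction's rationale for anemia is that vitamin D acts on iron homeostasis and red-cell formation. Cord iron may then lie on the pathway, and adjusting for it, or keeping only infants not anemic at birth, could remove part of the effect being sought. This stands. It rules out replacing the unadjusted result with the adjusted one, but it does not justify leaving the cord values unused, nor does it excuse omitting intake.

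A reader might also infer more than the documents support:
- That an infant already anemic at birth is counted as a new 6-month case. The plan has no anemia definition, cut-off or counting rule, and the general objective speaks of newborns, so the cord count could itself be an outcome.
- That maternal iron is unmeasured. Third-trimester ferritin, serum iron and blood count are taken. They show status at one time rather than intake, and say nothing about the infant after birth, but with the cord values they reduce what maternal intake questions would add.
- That baseline adjustment is free. Step 4 shows that precision can fall when cord iron and vitamin D are correlated, which is the very case that causes the bias.
- That a bias of known size is present. Nothing in the documents shows that families with higher vitamin D use more iron.

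The lack of any adjusted analysis is also general: Data Analysis assigns no named variable to any test, and iron is one instance. Finally, the Workflow figure is not shown, so statements of absence cover the text only.

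**Conclusion.** The concern holds in a limited form. The text records no iron intake for mother or infant, objective e does not match step 7, and neither the cord nor the maternal iron measurements have a stated role in the analysis. An anemia association found with the planned tests could not be separated from iron, and a null result could hide an effect.

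The size is unknown. The error rates of about 8% to 50%, and the ratios of 0.75 to 1.63, illustrate assumed correlations and uptake; with no link between iron and vitamin D the error stays near 5% and the ratio at 1.00. The change is worth making because it is cheap, not because a large bias has been shown.

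**What to change.** 1. Add cord blood count, ferritin and serum iron to Specific Objective e so that it agrees with step 7. This costs wording only.
2. Report the association of cord vitamin D with 6-month hemoglobin and with log ferritin twice: unadjusted, and adjusted by regression for the matching cord value. Add maternal ferritin as a further covariate only if 100 infants can support it. State that the unadjusted result includes any effect acting through iron status at birth and that the adjusted result removes it. Show anemia among infants not anemic at birth only as a secondary description; this needs a definition of anemia at each age, fixed in advance.
3. Ask about maternal iron or multivitamin use at enrolment and delivery. At the existing 3- and 6-month interviews ask about infant iron: drops, fortified formula or food, start date and reason. Use infant iron only in a sensitivity analysis, noting that it arises after exposure and may be started because hemoglobin is low.

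Costs: a few more questions, imperfect recall, possible over-adjustment, and some loss of precision if cord iron and vitamin D are correlated. Little extra data should be lost for ferritin, which shares the cord tube with vitamin D; the blood count comes from the other tube and can be missing on its own.
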